6.2.2 Blinding procedures

During the first phase, the allocation of the arm « control message » or of the arm « intervention message » will be determined by a code written on a card inside a sealed and opaque envelope, prepared by the principal investigator. This code will indicate the number, between 1 and 130, of the audio track to be played to the patient and will be recorded in the CRF. In the second phase, the note « control message » or « intervention message » written on the card will indicate to the caregivers the message to be delivered and will be reported in the CRF. Envelopes will be numbered consecutively, and the co-investigators will open them consecutively, noting each time the opening date. The principal investigator will regularly verify that the order of opening is respected by checking the number of envelopes opened and the opening dates against the number of patients included in the study.

The first phase of the study will be carried out in double blind (patient, caregiver, co-investigator) thanks to the coding of audio recordings. In the second phase, only patients will be blinded to the tested component.

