7.4 Criteria for withdrawal / discontinuation of participants

Patients will be excluded from the study if they are aware of the tested component or of the messages' content prior to the intervention. They will also be excluded if they meet one of the exclusion criteria (e.g. instability, loss of decision-making capacity) before they can sign the consent form.

Patients will also be excluded from the study if caregivers or co-investigators have been made aware of their message prior to the intervention.

Differences in the script, patient or caregiver interventions will be reported in the CRF under the « Difficulty(-ies) encountered » category for inclusion in the data analysis but will not be grounds for exclusion from the study. The same will be true in the second phase for variations in the messages delivered by caregivers. They will be reported in the CRF under the « Verbal script » category but will not constitute grounds for exclusion from the study.

Patients may choose to revoke their consent at any time. If they do so, they will be removed from the study.

Data collected from patients who are excluded or who have revoked their consent will be physically

destroyed using a shredder, with the exception of data relating to their sex and age, which will be reported for statistical purposes (Appendices 8 and 7). Patients will receive a complete information sheet so that they can contact the investigators if they wish to do so.

Excluded patients or patients who have revoked their consent will be included in the calculation of the number of participants required to complete the collection of study data, but a 10% mark-up of this number is expected to compensate for these missing data.

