11.4 Planned Analyses

Descriptive data will be presented by mean and standard deviation, median and interquartile space or proportions for Gaussian, non-Gaussian and categorical continuous variables. The comparison between randomized groups will be done by Student t-test or Wilcoxon rank sum test for continuous variables, and by Chi2 or Fisher for categorical variables, as appropriate.

The analyses will be performed using Stata software version 14 (StataCorp, TX, USA). The analysis will be performed by the principal investigator. To ensure that he is not aware of the assignment of patients to the intervention or control group, co-investigators will delete the patient number corresponding to that of the randomization list before the database is transmitted. Thus, the analysis of the data will be done blind. It is therefore a triple-blind study.

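### The envelope check in Section 6.2.2 uses only counts and dates, so in phase 2 it cannot confirm opening order within a day or that a patient was enrolled before the arm was seen

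*Combined protocol and SAP*

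**What the plan says.** Allocation uses sealed, opaque envelopes prepared by the principal investigator, who does not collect data (Sections 6.2.1 and 6.2.2). On their use, Section 6.2.2 says: "Envelopes will be numbered consecutively, and the co-investigators will open them consecutively, noting each time the opening date". The principal investigator regularly verifies the order "by checking the number of envelopes opened and the opening dates against the number of patients included in the study".

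The card differs by phase. In phase 1: "This code will indicate the number, between 1 and 130, of the audio track to be played to the patient". In phase 2, "the note « control message » or « intervention message » written on the card will indicate to the caregivers the message to be delivered", and "In the second phase, only patients will be blinded to the tested component".

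The prescribed sequence is eligibility, verbal consent, then randomisation (Study Schedule; Sections 6.1, 6.2.1 and 7.3). Co-investigators screen, take verbal consent and open the envelope, and only one of them is present at each intervention (Section 6.1). Patients can still leave the study after randomisation. Section 7.4 says "They will also be excluded if they meet one of the exclusion criteria" before they can sign the consent form, and patients may also revoke consent. The data of both groups are shredded except for sex and age.

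Two other places bear on traceability. Section 11.4 says "co-investigators will delete the patient number corresponding to that of the randomization list" before the database goes to the analyst, so a number linking patient and list exists. Section 12.3 has the monitor verify, among other items, the intervention date and the message received for each patient.

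**The concern.** The stated purpose of the check is to confirm that the opening order was respected. A calendar date does that across days but not within a day. Recruitment runs seven days a week from 7am to 10pm, so several patients on one date are possible. Order is also only half of concealment. The other half is that the patient was committed to the trial before anyone enrolling could see the arm. Section 6.2.2 asks for no clock time and for no patient identifier on the envelope before it is opened.

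In phase 2 the person who decides whether to enrol is not blind and reads the arm in plain words on opening. If enrolment followed opening, the choice of patient could depend on the arm, and the comparison of pain scores in that phase would lose the protection of randomisation without the check showing it.

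**Working it through.** **1. What the check can see.** The inputs are those of Section 6.2.2: envelope number, opening date and number of patients included. Take envelopes k and k+1 and candidate patients A and B.

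| Event | Record left | Result of the check |
|---|---|---|
| k opened for A, then k+1 for B, each after consent | two envelopes, same date, two patients | passes, correctly |
| k+1 opened on an earlier day than k | dates out of sequence | detected |
| k and k+1 opened in reverse order on one day | two envelopes, same date, two patients | passes |
| k opened before A is enrolled, arm seen, A not enrolled, k used for B that day | one envelope, one patient, matching date | passes |
| k opened for A, A then excluded or revokes consent | one opened envelope without an included patient | surplus of one, cause unknown |

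Rows three and four are the gap. Row four is harmful only if opening shows the arm, which is so in phase 2 but not in phase 1.

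**2. How informative a surplus is.** Section 11.2 gives 60 randomised per arm, so 2 × 60 = 120 per phase and 4 × 60 = 240 in all. It allows 10% for missing values or refusal after randomisation, and Section 7.4 applies a 10% mark-up for exclusions and revocations. In phase 2, 0.10 × 120 = 12, so up to about 12 surplus envelopes would look ordinary. A few selective exclusions would not stand out. Section 7.4 also counts excluded and revoking patients towards the number required. If they were counted as included in this check too, there would be no surplus at all.

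**3. What the rest of the protocol adds.**
- Section 6.1 puts the patient identification number first in the CRF order, before the eligibility criteria. That suggests it is assigned early, but the heading there is only before insertion, and the list contains no envelope number and no randomisation time.
- The patient number matches the list (Section 11.4) and the track code or message is written in the CRF (Section 6.2.2). These could be compared, but the check in Section 6.2.2 does not use them.
- The monitor's items (Section 12.3) include no envelope number and no opening time.

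**4. How often dates would coincide (illustration).** If N patients fall independently and evenly over D days, the share with at least one other patient on the same date is 1 − (1 − 1/D)^(N−1). N = 120 comes from the plan. D is assumed, because neither the length of phase 2 nor the number of recruiting days is given; 365 is half of the two-year study.

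| D (assumed) | Calculation | Share |
|---|---|---|
| 365 | 1 − (364/365)^119 | 28% |
| 240 | 1 − (239/240)^119 | 39% |
| 120 | 1 − (119/120)^119 | 63% |
| 60 | 1 − (59/60)^119 | 86% |

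This is the share of patients whose order a date cannot settle. It does not measure row four, which needs only a second candidate that day, enrolled or not; the plan gives no count of candidates.

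**5. Effect on the plan's figures.** The sample size reproduces. With a difference of 13 mm, SD 24 mm, 80% power and two-sided alpha 0.05, the normal formula gives 54 per arm and the t-based one 54.5, rounded up to the stated 55. Nothing in this point changes it.

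**The case against.** The main safeguards are in place: sealed opaque envelopes, prepared by someone who collects no data, numbered consecutively, with blocks of 4 and 6, opened after verbal consent and checked regularly. That stands. The gap is in verification, and the rule itself is sound.

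The count also has real value. A reader might infer that an exclusion made after opening is invisible. The documents do not support that: an exclusion before opening uses no envelope, whereas one after opening leaves a surplus, provided the patient is not counted as included. Excluded and revoking patients are also recorded in separate documents (Appendices 7 and 8), so numbers can be reconciled. What remains hidden is whether the reason had to do with the arm.

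A reader might also infer that a same-day exchange of envelopes is untraceable. That is too strong. If the patient number was fixed beforehand, an exchange could appear as a mismatch between the CRF and the list. The data for that comparison exist, but the stated check does not call for it, and it would not reveal an envelope opened early and then used for the next patient in turn.

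Exclusion under Section 7.4 is not wholly in the co-investigator's hands either. Its examples are instability and loss of decision-making capacity, and under Section 7.1 instability can be judged by the treating physician.

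Finally, the co-investigator would make the added entries, so they are not independent proof. This is correct and limits what the fix can achieve.

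**Conclusion.** The point holds as a cheap improvement, mainly for phase 2. The check in Section 6.2.2 cannot order envelopes within a day and cannot show that enrolment came before opening. In phase 2 the enrolling co-investigator sees the arm on opening, so an envelope opened early and kept for another patient that day could pass. In phase 1 only a coded track number is seen, and the concern is limited to order.

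No bias can be put in figures from the documents. About 28% of phase 2 patients sharing a date rests on random recruitment over an assumed 365 days. The higher shares rest on shorter recruitment periods, also assumed. A reader might take these percentages as a rate of selection, or take the gap as a sign that concealment failed. Neither follows: a shared date is not a breach, and the plan prescribes the right sequence.

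The conclusion rests on the protocol text. The CRF and appendix forms are not reproduced, so a time or envelope field on one of them cannot be ruled out. If one exists, Section 6.2.2 should refer to it.

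**What to change.** In Section 6.2.2:

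- Before opening, the co-investigator writes the patient identification number, date and clock time on the sealed envelope and on a sequential log.
- Opened envelopes are kept.
- Each exclusion or revocation after randomisation is logged with its envelope number and time.
- The principal investigator reconciles envelope number, patient number, time and the message or track recorded in the CRF against the randomisation list, in place of counts and dates alone.

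The cost is a few seconds per patient, one log sheet and a short change of wording. Sample size, alpha and analysis are unaffected. The record still depends on the co-investigator completing it before opening, so it makes a departure harder to hide but does not exclude one.

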6.2.3 Other methods of minimising bias

Based in particular on the limitations identified from the studies included in the 2015 systematic review (Mistiaen et al., 2016), the following measures were taken to minimize as much as possible the bias that could result from this study:

- Integrity of the intervention: most of the studies included in the systematic review had not verified the accuracy of their intervention. In both phases of our study, caregiver behaviour will be reported in the CRF according to Kaptchuck criteria. In the first phase of the study, caregivers will be instructed to act naturally with patients during the procedure, without referring to the ongoing study throughout the entire duration of the procedure or commenting early on the PIC placement. Any interactions will be reported in the CRF under the « Difficulty(-ies) encountered » category. In the second phase, the script as it has been verbalized by the caregivers will also be globally reported. The content of the message delivered by caregivers will be reported in writing to the CRF as key words/concepts, checked off once they have been stated. For key words/concepts that would not be included in the original script, but which would still be mentioned by caregivers, they will be reported specifically under the « Other(s) » category. We have also scheduled for each phase an information session for the emergency care staff on the progress of the study and the content of the messages at one of their monthly team meeting, which will then be the subject of a report sent to the entire team;
- Statistical considerations: most of the studies included in the systematic review had not calculated an *a priori* statistical power, and since many studies included a small number of patients (from 19 to 771 with an average of 110 patients per study), divided into several intervention arms, the probability was high that a real effect could not be detected. We calculated an *a priori* statistical power in our study and set a minimum number of participants at 240;
- Retention of baseline demographic data (sex, age) of patients who have revoked consent or who were excluded from the study to ensure that they are similar to patients included on these

two criteria;

- Intervention control not described: we plan to transcribe the texts of the messages intervention and control in the presentation of the results of the study;
- Lack of blindness: the risk of bias was considered significant in most of the studies included in the systematic review due to the lack of blindness of practitioners, patients and observers. However, our study will be done in double blind during the first phase, then simple blind for the second. Furthermore, in both phases, patients will initially not be informed of the fact that the study's purpose is communication, let alone that two alternative messages will be tested, which limits bias in their evaluations;
- Use of validated tools wherever possible;
- Reporting of patient behaviour during the PIC insertion;
- Playing of a test audio clip, preceding the audio messages recorded and common to all participants, so that the sound level can be adjusted appropriately;
- Pilot phase « Messages » - Reactions to the listening of recorded audio messages;
- Pilot phase « Rating » - Evaluation of the ability of the co-investigators to rate the same way identical behaviour.

6.3 Unblinding Procedures (Code break)

Only the principal investigator will hold the coding key and it will only be revealed once all the data has been collected, entered into the database and statistically analyzed.

In case of an urgent situation, the allocation to one of the arms can be obtained from the principal investigator.

7. STUDY POPULATION

7.1 Eligibility criteria

Patients meeting all of the following inclusion criteria will be eligible to participate in this study:

- Patient ≥ 18 years old;
- Patient whose management requires the placement of a first PIC;
- Placement of the PIC on the upper limb.

Patients with any of the following criteria will be excluded from the study:

- Clinically unstable patient (passing through the resuscitation room or judged as such by the physician in charge of the case);
- Patient without decision-making capacity or with whom it is difficult to communicate:
 - Altered mental status (e.g. cognitive impairment, mental retardation, acute confusion state, acute psychosis);
 - Altered mental status due to recreational drug use;
 - Intoxication;
 - Patient unable to sufficiently communicate in French to give informed consent and answer questions about pain and anxiety;
 - Hearing impaired patient;
- Patient unable to use the rulers (e.g. blind patient);
- Altered upper limb (e.g. sensitivity disorders, lymphoedema);
- Incarcerated patient;
- Patient transferred from another hospital;
- Patient who has already participated in this study during a previous consultation;
- Patient who knows the tested component (i.e. clinical communication) before the intervention;
- Patient, caregiver or co-investigator who knows the content of the message assigned before the intervention (for the first phase of the study).

7.2 Recruitment and screening

All patients admitted to the LUH ED between October 2017 and October 2019 will be eligible for inclusion. A first evaluation of the inclusion and exclusion criteria by the co-investigators will be based on the patient's medical file in the ED and a discussion with the caregivers in charge of the case. These criteria will be re-evaluated by the co-investigators at the patients' bedside.

Participation in this study will not be remunerated.

7.3 Assignment to study groups

After verifying that all inclusion criteria have been met, that none of the exclusion criteria are applicable and that each participant has given his or her verbal consent, each participant will be randomized in a 1:1 ratio between the two arms of the study using the opaque and sealed envelopes mentioned in section 6.2.2 « Blinding procedures ».

7.4 Criteria for withdrawal / discontinuation of participants

Patients will be excluded from the study if they are aware of the tested component or of the messages' content prior to the intervention. They will also be excluded if they meet one of the exclusion criteria (e.g. instability, loss of decision-making capacity) before they can sign the consent form.

Patients will also be excluded from the study if caregivers or co-investigators have been made aware of their message prior to the intervention.

Differences in the script, patient or caregiver interventions will be reported in the CRF under the « Difficulty(-ies) encountered » category for inclusion in the data analysis but will not be grounds for exclusion from the study. The same will be true in the second phase for variations in the messages delivered by caregivers. They will be reported in the CRF under the « Verbal script » category but will not constitute grounds for exclusion from the study.

Patients may choose to revoke their consent at any time. If they do so, they will be removed from the study.

Data collected from patients who are excluded or who have revoked their consent will be physically

destroyed using a shredder, with the exception of data relating to their sex and age, which will be reported for statistical purposes (Appendices 8 and 7). Patients will receive a complete information sheet so that they can contact the investigators if they wish to do so.

Excluded patients or patients who have revoked their consent will be included in the calculation of the number of participants required to complete the collection of study data, but a 10% mark-up of this number is expected to compensate for these missing data.

8. STUDY INTERVENTION

8.1 Identity of Investigational Products

Regarding the first phase of the study:

- In order to adjust the sound volume properly, a test audio clip will be played to the patients. It will have the following content: « Hello. Thank you for your participation in this study. This is a sound volume test. Please tell the staff if you can hear me well, or if there's a problem. »
- An introductory sequence, identical for both groups, will also be played to the participants before the caregivers prepare them for the procedure (placement of the tourniquet, identification of the vein and site disinfection). It will have the following content: « This is a standard message regarding the following procedure, thank you for listening. As part of your medical care, the placement of a venous catheter is necessary. The caregiver will prepare your arm for the procedure. »
- The intervention and control messages will be played to patients once the caregivers have completed their preparations and are ready to sting the patients.

8.1.1 Experimental Intervention

First phase - Text of the recorded intervention message:

In the « intervention message » arm, the recorded message will be:

« It is possible that this arm may begin to feel a certain numbness, a kind of heaviness, or warmth, as if it was asleep during the procedure. Now that you've heard this message, you can signal the caregiver as soon as you're ready by lifting a finger from your other hand. »

The key elements are: dissociation of the arm, being ready, sense of control, anesthetic suggestion limited to the duration of the procedure.

Second phase - Text of the intervention message delivered by caregivers:

In order for the intervention to be credible, it is important that caregivers take ownership of the message to be delivered. Caregivers will then receive the original text, along with the key elements it contains and the contradictory elements to be omitted. They will be encouraged to formulate a variant that fits them but contains these key elements. A reminder of key elements will be provided at each clinical interaction. Some deviations from the script will be tolerated as long as the essential content of the message to be delivered is preserved and no contradictory elements are inserted. The content of the messages delivered by caregivers will be reported in writing in the CRF by the co-investigator in the form of key words/concepts, checked off once they have been stated. For key words/concepts that would not be included in the original script, but which would still be mentioned by caregivers, they will be reported specifically under the « Other(s) » category.

8.1.2 Control Intervention

First phase - Text of the recorded control message:

In the « control message » arm, the recorded message will be:

« You may feel the tourniquet on your arm, it's tight, maybe it's tingling. Stinging can hurt when the needle goes in, but don't move during the procedure. When this message stops, lift a finger from your other hand and the caregiver will sting you. »

The key elements are: contact with the tourniquet and its sensory aspect, then sensory aspects of the needle, lack of control.

Second phase - Text of the control message delivered by caregivers:

Similar to the text of the intervention message delivered by the caregivers in section 8.1.1 « Experimental intervention ».

